B	SCR up to 90 days	RND	Symptomatic nonhormonal medical treatment as determined by the investigators and/or watch and wait														12 wk FUP	

Groups A1, A2, and A3 treated daily with vilaprisan 2 mg during treatment periods
 Group A1: 4/8 treatment periods of 12 weeks, each separated by 1 bleeding episode (3/1 regimen)
 Group A2: 2/4 treatment periods of 24 weeks, separated by 2 bleeding episodes (6/2 regimen)
 Group A3: 3/6 treatment periods of 12 weeks, each separated by 2 bleeding episodes (3/2 regimen)
 Group B treated with standard of care (SoC) symptomatic nonhormonal medical treatment as determined by the investigators and/or watch and wait.
 B = bleeding episode; FUP = follow-up; RND = randomization; SCR = screening; trt = treatment; wk = week.

The **primary safety variable** is the percentage change in bone mineral density (BMD) of lumbar spine from baseline to about one year after start of treatment (SoT) (please refer to section 6.5.1 for details). With the implementation of Protocol Amendment 10 (version 7.0), the study is being prepared for closure. A thorough safety monitoring is performed in subjects before this closure, including a recovery BMD scan. All subjects who received vilaprisan treatment will be asked to undergo a BMD scan at least 6 months after the last intake of vilaprisan, to document absence of

bone loss or adequate recovery after the end of treatment. Subjects randomized to treatment group B who are still in the study with implementation of Protocol Amendment 10 (version 7.0) should also undergo a BMD scan at the safety closeout visit, unless they had a BMD scan performed within the last 3 months prior to the safety closeout visit.

4. General Statistical Considerations

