6.5.1 Primary safety variable

The primary safety variable is the percentage change in BMD of lumbar spine (using the central reading results) from baseline to about one year after SoT. One year is defined as ‘Month 12 on treatment’ in Table 6-1, i.e. Day 300 after reference start date to Day 420 after reference start date, but no later than the reference end date + 60 days.

The primary safety variable will be analyzed using descriptive statistical methods and two-sided 95% confidence interval (CI) for the mean difference for the percentage change in BMD of lumbar spine from baseline to about one year after SoT will be calculated for each vilaprisan treatment group as compared to treatment group B. Additionally, two-sided 95% CI for each treatment group will be calculated. The primary variable is assumed to be at least approximately normally distributed.

For the percentage change in BMD of lumbar spine from baseline to other time points defined in Table 6-1, the descriptive statistics will also be provided by treatment group.

The percentage change in BMD of lumbar spine from EoT BMD will also be evaluated using summary statistics by treatment group and time interval or month for post treatment period defined in Table 6-1.

The time intervals and month named in Table 6-1 will be presented in tables and figures unless otherwise specified. Month equals 30 days.

Table 6-1: Definition of month and time intervals for BMD summary

	Month	Time interval
Baseline	Baseline	Baseline if no Visit 2-repeat scan exists, Visit 2 scan will be used as baseline. Otherwise, Visit 2 -repeat scan will be used. The BMD baseline visit will be marked in the dataset transferred from ICON’s Medical Imaging group. (refer to section 4.5)
On treatment period : From reference start date to reference end date + 60 days	Month 1	N/A
	Month 2	If a BMD value performed after the reference start date has been marked as baseline value, it will be analyzed as baseline value and will be excluded from the analysis for on treatment period.
	Month 3	
	Month 4	
	Month 5	Month 6 on treatment Day 120 after reference start date to Day 240 after the reference start date, but no later than the reference end date + 60 days
	Month 6	
	Month 7	
	Month 8	
	Month 9	N/A
	Month 10	Month 12 on treatment Day 300 after reference start date to Day 420 after reference start date, but no later than the reference end date + 60 days
	Month 11	
	Month 12	
	Month 13	
	Month 14	

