	>Month 14	N/A In case of more than one measurement > Month 14, the worst measurement within the time interval will be used for calculations.

	N/A	EoT BMD Reference end date ± 60 days If two measurements are available during the EoT BMD time interval, the measurement closest to the reference end date will be use as EoT BMD measurement.
Post treatment period: After reference end date + 60 days	Month 3	N/A
	Month 4	Month 6 post treatment
	Month 5	Day 120 after the reference end date to Day 240 after the reference end date
	Month 6	
	Month 7	
	Month 8	
	Month 9	N/A
	Month 10	Month 12 post treatment
	Month 11	Day 300 after the reference end date to Day 420 after the reference end date
	Month 12	
	Month 13	
	Month 14	
	>Month 14	N/A In case of more than one measurement > Month 14, the worst measurement within the time interval will be used for calculations.
	N/A	EoFUP BMD The last measurement, but no earlier than the reference end date + 60 days

BMD = bone mineral density; EoT=end of treatment; EoFUP= end of follow-up; N/A=not applicable

Percentage change in BMD of lumbar spine from baseline with frequencies and percentages for the following categories: <-6%, ≥-6% - <-3% , ≥-3% - <-1.5% , ≥-1.5% - ≤0%, >0% - ≤1.5%, >1.5% - ≤3% , >3% - ≤6% and >6% will also be summarized by treatment group. The worst outcome per subject during treatment period will be used in the analyses.

Frequency table for the status of BMD of lumbar spine at EoFUP compared with EoT will be provided by treatment group. The categories for the status of BMD of lumbar spine at EoFUP is defined in Table 6-2. Percentage of recovery is defined as change in BMD of lumbar spine from EoT BMD to EoFUP BMD divided by change in BMD of lumbar spine from Baseline to EoT BMD. It will be evaluated in subjects with partially recovered. Number and percentage of subjects for percentage of recovery by categories of ≥ 75 - < 100%, ≥ 50 - <75%, ≥ 25 - <50% and ≥ 0 - <25% will be provided for subjects with partially recovered.

Table 6-2: Status of BMD of lumbar spine at EoFUP

% change in BMD of lumbar spine from baseline to EoT BMD (x)	% change in BMD of lumbar spine from baseline to EoFUP (y)	Status at EoFUP	Percentage of recovery
< 0	≥ 0	Recovered, completely	≥ 100%

< 0	$x \leq y < 0$	Recovered, partially	$\geq 0\% - <100\%$
< 0	$y < x$	Not recovered or further decrease	Not applicable
≥ 0	≥ 0	No decrease during both treatment and FUP period	Not applicable

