6.5.2.2 Endometrial thickness

For endometrial thickness the following time intervals will be considered:

- Intervals A (according to [Figure 4-1](#))
- Intervals C (according to [Figure 4-1](#))
- Exit examination

Number of subjects with ultrasound performed will be presented.

Summary statistics for change from baseline in endometrial thickness will be provided. In addition, the proportion of subjects with endometrial thickness > 18 mm will be investigated. A subgroup analysis by exposure group (treatment duration <=90 days, 91 to 180 days, etc.) will present the proportion of subjects with endometrial thickness > 18 mm and cyst like structure either ovary >= 3cm.

To investigate the correlation of endometrial thickness and biopsy results, the proportion of biopsies with hyperplasia without atypia (WHO 2014), atypical hyperplasia / EIN (WHO 2014), PAEC

present, PAEC not present, Extensive cysts present, and Extensive cysts not present will be presented for endometrial thickness > 18mm in ultrasound and endometrial thickness ≤18 mm in ultrasound.

6.5.2.3 Percentage change from baseline in BMD measured, hip, and femoral neck by DEXA

The percentage change in BMD of hip, and femoral neck will be summarized in the same way as described for the primary safety variable.

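### The BMD percentage-of-recovery formula has the wrong sign and cannot give the values that its own bins and Table 6-2 require

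*SAP*

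**What the plan says.** SAP Section 6.5.1 plans a frequency table of lumbar spine BMD status at EoFUP compared with EoT, with categories set in Table 6-2. The table uses x, the percentage change from baseline to EoT, and y, the percentage change from baseline to EoFUP.

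- Complete recovery: x < 0 and y ≥ 0, with percentage of recovery given as at least 100%.
- Partial recovery: x < 0 and x ≤ y < 0, with percentage of recovery given as 0% to below 100%.
- All other rows: percentage of recovery not applicable.

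The percentage itself is the "change in BMD of lumbar spine from EoT BMD to EoFUP BMD divided by change in BMD of lumbar spine from Baseline to EoT BMD". On the population the SAP says: "It will be evaluated in subjects with partially recovered". Counts are then planned "by categories of ≥ 75 - < 100%, ≥ 50 - <75%, ≥ 25 - <50% and ≥ 0 - <25" percent.

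Two other places bear on this. Section 3 explains that vilaprisan-treated subjects are asked for a scan at least 6 months after last intake, to document absence of "bone loss or adequate recovery after the end of treatment". Section 6.5.2.3 says that hip and femoral neck BMD "will be summarized in the same way as described for the primary safety variable".

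**The concern.** The numerator and denominator run in opposite directions for anyone who lost bone on treatment and regained some afterwards. The first change is upward, the second downward, and nothing in the definition reverses a sign or takes an absolute value. A ratio of a gain to a loss is negative, yet every bin and every range attached to it is zero or positive.

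If the rule were programmed as written, the four bins would be empty apart from subjects whose EoFUP value exactly equals their EoT value. This is the only planned output that expresses an individual's regain as a share of that individual's loss, which is close to the question the post-treatment scan was requested to answer.

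**Working it through.** **Inputs.** The definition, the restriction to partially recovered subjects and the bins come from the text of Section 6.5.1. The conditions on x and y and the two percentage ranges come from Table 6-2. BMD values below are illustrative, because the SAP contains no results.

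**Step 1: the formula in Table 6-2 terms.** With baseline B, EoT = B(1 + x) and EoFUP = B(1 + y), taking x and y as fractions:

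written ratio = (EoFUP − EoT)/(EoT − B) = (y − x)/x = y/x − 1.

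B cancels, so absolute BMD change and change as a percentage of baseline give the same value.

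**Step 2: can it reproduce the table's ranges?**

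- Partial recovery (x < 0, x ≤ y < 0): y/x lies in (0, 1], so the ratio lies in (−100%, 0%]. The table says 0% to below 100%. The two meet only at y = x.
- Complete recovery (x < 0, y ≥ 0): y/x ≤ 0, so the ratio is −100% or lower. The table says at least 100%. The two never meet.

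**Step 3: with the denominator reversed.**

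(EoFUP − EoT)/(B − EoT) = 1 − y/x.

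This lies in [0%, 100%) for partial recovery and is at least 100% for complete recovery, which matches both table ranges.

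**Step 4: numbers.** Baseline 1.000 and EoT 0.950, so the written denominator is −0.050 and the reversed one +0.050.

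| EoFUP | EoFUP − EoT | As written | Denominator reversed | Where it belongs |
|---|---|---|---|---|
| 0.955 | 0.005 | −10% | +10% | 0 to <25% |
| 0.970 | 0.020 | −40% | +40% | 25 to <50% |
| 0.980 | 0.030 | −60% | +60% | 50 to <75% |
| 0.990 | 0.040 | −80% | +80% | 75 to <100% |
| 1.010 | 0.060 | −120% | +120% | complete, ≥100% |

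The written ratio is positive only when bone loss continues after treatment. With x = −4% and y = −5% it is (−5 + 4)/(−4) = +25%, a row that Table 6-2 marks as not applicable.

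**Step 5: does another reading of change rescue it?** Taking each percentage change relative to its own starting value leaves the sign negative. With x = −4% and y = −2.5% the numerator is 0.015/0.96 = 1.5625% and the ratio is 1.5625/(−4) = −39.06%.

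**Step 6: the scale also needs stating.** Section 6.5.1 separately plans this variable: "The percentage change in BMD of lumbar spine from EoT BMD will also be evaluated using summary statistics". If it were used as numerator over the loss as a percentage of baseline, with the sign repaired, then x = −5% and y = −0.1% would give (0.049/0.950)/0.050 = 103%. That is outside the bins for a subject classed as partially recovered. On a common scale the value is 1 − 0.1/5 = 98%.

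**The case against.** The strongest reply is that the intent is not in doubt. The population, the bins and the Table 6-2 column stand next to the formula, and only the regained share of the loss fits them all. A literal program would also expose itself, because the bin counts would not add up to the number of partially recovered subjects. Recovery is documented in other ways too: percentage change from EoT by post-treatment interval, and a listing of subjects with a loss of 3% or more at EoFUP. The ratio is evaluated only in partially recovered subjects, so the mismatch for complete recovery affects a table label and no planned output. Finally, Section 6.5.2.3 speaks of the percentage change at hip and femoral neck, while the recovery text and the title of Table 6-2 name the lumbar spine.

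Much of this stands as a limit on the weight of the point. It does not remove the error. Change is signed throughout this part of the SAP: Table 6-2 writes x < 0, and the change categories run from below −6% to above 6%. Where a magnitude is meant, the SAP speaks of loss or decrease. The other outputs describe recovery but do not scale it to the individual's loss. Extending the point to the other two sites is a fair reading of the cross-reference, though the SAP does not spell it out. The mixed-scale risk is smaller, since the definition uses the same term for both changes, but a few words close it.

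**Conclusion.** The definition is wrong as written. For every partially recovered subject it gives zero or a negative value, and it contradicts the four planned bins and both ranges in Table 6-2. The conclusion rests on reading change as later value minus earlier value, which is how the SAP uses it in the same table. It needs no assumption about the trial data.

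The consequence is limited. Status at EoFUP is assigned from x and y directly, so those counts do not change, and the primary 12-month BMD comparison does not use the ratio. What is affected is the descriptive breakdown of partial recovery at the lumbar spine, and at hip and femoral neck if it is repeated there. It should be corrected because it is a stated derivation rule that gives wrong values if followed.

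**What to change.** In Section 6.5.1, define percentage of recovery as (EoFUP BMD − EoT BMD)/(baseline BMD − EoT BMD) × 100, equivalently (1 − y/x) × 100 in the notation of Table 6-2. Add that both changes are absolute BMD changes, or both are percentages of baseline, and that the separate percentage change from EoT is not the numerator. In Section 6.5.2.3, state whether the recovery table is repeated for hip and femoral neck and, if so, that the same formula applies.

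The cost is one formula line and a short clarification. The bins and Table 6-2 stay as they are, and no data, table or analysis is added.

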≥ 0	< 0	No decrease during treatment period but worsening during FUP period	Not applicable

Mean-deviation plot for the percentage change in BMD of lumbar spine from baseline will be presented by treatment group for the entire study period (treatment period + post treatment period).

Following listings will be provided separately:

- 1) subjects that had at least one DEXA scan during the treatment period with either BMD loss $\geq 6\%$ from baseline to EoT for any location or Z-score ≤ -2 SD for any location.
- 2) subjects with BMD loss $\geq 3\%$ from baseline for any location or Z-score ≤ -2 SD for any location at EoFUP DEXA scan.

During the study, if the baseline scan at Visit 2 was missing or not evaluable based on the evaluation from the Medical Imaging group of ICON, the subject was requested to have a repeat scan. If it's not possible to have this repeat scan performed before the reference start date, this repeat scan was allowed to be performed shortly after the start of the treatment. Considering the BMD will not change quickly, this can be accepted from a medical point of view. If a BMD value performed after the reference start date has been marked as baseline value, it will be analyzed as baseline value and will be excluded from the analysis for on treatment period defined in Table 6-1.

To make a further investigation, an additional analysis for the primary safety variable with subjects excluded who had their baseline scan later than 1 month after start of treatment will be provided.

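### Table 6-2 reports no decrease in follow-up for subjects whose lumbar spine BMD fell after end of treatment, because one row never compares EoFUP with EoT

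*SAP*

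**What the plan says.** SAP section 6.5.1 introduces the table with this sentence: "Frequency table for the status of BMD of lumbar spine at EoFUP compared with EoT will be provided by treatment group". Its two axes are headed "change in BMD of lumbar spine from baseline to EoT BMD (x") and "change in BMD of lumbar spine from baseline to EoFUP (y"), so both are measured from baseline and cut at exactly zero. The five rows are:

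| x (EoT) | y (EoFUP) | Status | y compared with x? |
|---|---|---|---|
| < 0 | ≥ 0 | "Recovered, completely" | not needed, since y > x follows |
| < 0 | x ≤ y < 0 | "Recovered, partially" | yes |
| < 0 | y < x | "Not recovered or further decrease" | yes |
| ≥ 0 | ≥ 0 | "No decrease during both treatment and FUP period" | no |
| ≥ 0 | < 0 | "No decrease during treatment period but worsening during FUP period" | not needed, since y < x follows |

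The last column is added here. Section 6.5.2.3 applies the methods of the primary safety variable to hip and femoral neck. Section 5.1 repeats all BMD endpoints in the modified SAF.

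**The concern.** In four of the five rows the direction of change from EoT to EoFUP is either tested or follows from the signs of x and y. The fourth row is the exception. It holds subjects who rose, stayed level or fell after EoT, and it describes all of them as having had no decrease in follow-up.

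Section 3 gives the purpose of the recovery scan as documenting that bone was not lost, or recovered adequately, after vilaprisan. It states that purpose for the scan and not for this table. Still, Table 6-2 is the only place in section 6.5.1 where each subject receives a status describing what happened after treatment. A status that is wrong for a definable set of subjects errs in the reassuring direction.

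**Working it through.** The SAP states no figure for this table, so there is none to reproduce. The check applies the table as a rule.

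**1. Is the label true for every subject in the row?**

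Set baseline BMD to 100. Then EoT = 100 + x, EoFUP = 100 + y, and the change over follow-up is (100 + y)/(100 + x) − 1.

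- x = +4%, y = +0.5%: 100.5/104 − 1 = −3.4%
- x = +4%, y = +0.1%: 100.1/104 − 1 = −3.75%
- x = +5%, y = 0%: 100/105 − 1 = −4.76%

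All three receive the no-decrease status. In general the follow-up change is negative exactly when y < x, so the label is false for all of 0 ≤ y < x.

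**2. Do other planned outputs supply the missing count?**

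- Percentage change from EoT (section 6.5.1) is summarised by group and post-treatment interval. With the default statistics of section 4.1, the minimum would show the single largest fall. It would not show how many fell, or which of them were in this row.
- The second listing in section 6.5.1 takes subjects with a loss of at least 3% from baseline, or a Z-score of −2 or lower, at any location at EoFUP. A subject at +0.5% from baseline is not picked up on her lumbar spine change.

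**3. How often could this occur through measurement error alone?**

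Assume no true change, and independent, identically distributed errors at baseline (b), EoT (e) and EoFUP (f). The six orderings then each have probability 1/6:

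| Ordering | Status in Table 6-2 |
|---|---|
| e < b < f | complete recovery |
| e < f < b | partial recovery |
| f < e < b | not recovered |
| f < b < e | worsening in follow-up |
| b < f < e | no decrease in both, **although f < e** |
| b < e < f | no decrease in both |

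The fourth row receives 2/6 = 33.3% of subjects, and half of these fell after EoT. The result does not depend on the size of the error. Averaging two scans per time point (section 4.5) therefore does not alter these proportions.

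The same enumeration covers the x < 0 rows. Half of all subjects show an apparent loss, and (1/6 + 1/6)/(3/6) = two thirds of those are classed as completely or partially recovered.

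**4. Would a minimum loss at EoT cure the x < 0 rows?**

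The SAP gives no DEXA precision, so a per-visit error SD of 1% of BMD is assumed, with additive errors. The share of subjects entering the recovery rows who have y ≥ x, by simulation, is:

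| True course | Entry x < 0 | Entry x ≤ −1.5% | Entry x ≤ −3% |
|---|---|---|---|
| No change at any time | 67% | 81% | 92% |
| Permanent 2% loss, no recovery | 53% | 62% | 76% |

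A stricter entry rule admits fewer false decliners: with no true change, about 50%, 14% and 2% of subjects enter. Among those who enter, however, apparent recovery is more frequent, because selecting on an extreme x selects on error at baseline and at EoT. With a permanent 2% loss, the 3% rule also leaves out about 76% of subjects.

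**The case against.** The best defence of the row is that both column headings refer to baseline, so a decrease can be read as being below baseline. A careful reader would then take the row to mean at or above baseline on both occasions. On that reading the numbers are right and only the words are loose. This does not fully rescue the label. It speaks of a decrease during the follow-up period, the table is announced as a comparison with EoT, and two of the x < 0 rows do test y against x. The reference point therefore changes within one table. It is also fair to say that falls after EoT are not invisible, since the group summary of change from EoT is planned. What is missing is the count of subjects.

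A reader might go further and infer that the zero cut-offs invalidate the recovery rows, and that the main table should be limited to subjects with a loss of at least 3% (or 1.5%) at EoT. The documents do not support that. The table carries no test or decision rule. It is shown by treatment group including group B, where the same error operates. The 3% figure in the SAP belongs to a listing of loss at EoFUP and is not an entry rule at EoT. Such a restriction would also raise the share falsely classed as recovered, as step 4 shows.

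**Conclusion.** The defect in the fourth row stands and rests on no assumption: the status is false for every subject with 0 ≤ y < x, and no planned output gives their number. That number cannot be predicted from the SAP. The figure of half the row is the limiting case of no true change with equal, independent errors.

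The consequence is limited. The table is descriptive, and the Month 12 comparison of each vilaprisan group with group B is not touched. The effect of the zero cut-offs on the recovery rows is a caution for interpretation and does not justify replacing them. Two thirds of apparent decliners would be classed as recovered from error alone, under the same assumptions about error.

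**What to change.** Split the fourth row of Table 6-2 in two:

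- x ≥ 0 and y ≥ x: no decrease during treatment or follow-up.
- x ≥ 0 and 0 ≤ y < x: decrease after EoT, still at or above baseline.

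Apply the same split where the table is produced for hip and femoral neck (section 6.5.2.3) and in the modified SAF. Keep the recovery rows defined by x < 0 as the main display. At most, add a footnote that cut-offs at exactly zero produce some apparent recovery from measurement error alone, so the recovery frequencies in the vilaprisan groups should be read against those in group B.

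The cost is a wording change in the SAP and one extra row per table. No new data or derivation is needed, since x and y are already computed for every subject in the table.
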